11.3 Site monitoring

Before study initiation, at an initiation visit or at an investigator's meeting, a Novartis representative will review the protocol and data capture requirements (i.e. eSource DDE and/or eCRFs) with the investigators and their staff. During the study, Novartis employs several methods of ensuring protocol and GCP compliance and the quality/integrity of the sites' data. The field monitor will check the completeness of participant records, the accuracy of data capture / data entry, the adherence to the protocol and to Good Clinical Practice, the progress of enrollment, and to ensure that study treatment is being stored, dispensed, and accounted for according to specifications. Key study personnel must be available to assist the field monitor in conducting these activities. Continuous monitoring of each site's data will be performed throughout the conduct of the study. Additionally, a central analytics organization may analyze data & identify risks & trends for site operational parameters, and provide reports to Novartis clinical teams to assist with trial oversight.

The investigator must maintain source documents for each participant in the study, consisting of case and visit notes (hospital or clinic medical records) containing demographic and medical information, laboratory data, electrocardiograms, and the results of any other tests or assessments. All information on eCRFs must be traceable to the respective source documents.

The investigator must also keep the original informed consent form signed by the participant and/or legal representative (a signed copy is given to the participant).

The investigator must give the monitor access to all relevant source documents to confirm their consistency with the data capture and/or data entry. Source data verification may be done on-site, if possible, or remotely, if the field monitor does not have access or have limited access to the site due to the current COVID-19 pandemic. Different approaches can be used depending on site medical records, and some of them could include sharing the information through electronic systems or platforms provided by a third party. In all cases investigator and sponsor must adhere to the recommendations established by the applicable Health Authorities. Novartis monitoring standards require verification for the presence of all informed consents, adherence to the inclusion/exclusion criteria, documentation of SAEs, and of data that will be used for all primary variables. Additional checks of the consistency of the source data with the eCRFs are performed according to the study-specific monitoring plan. No information in source documents about the identity of the participants will be disclosed.

12 Data analysis and statistical methods

Any data analysis carried out independently by the investigator should be submitted to Novartis before publication or presentation.

12.1 Analysis sets

The Randomized Analysis Set (RAS) consists of all randomized participants.

According to the intent to treat principle, participants will be analyzed according to the treatment they have been assigned to during the randomization procedure.

The Safety Set includes all participants who received at least one dose of study treatment. Participants will be analyzed according to the study treatment received, where treatment received is defined as the randomized/assigned treatment if the participant took at least one dose of that treatment or the first treatment received if the randomized/assigned treatment was never received.

The analysis of the primary objective and all other efficacy variables will be performed on the RAS. The Safety Set will be used in the analysis of all safety variables.

12.2 Participant demographics and other baseline characteristics

Demographic and other baseline data including disease characteristics will be listed and summarized descriptively by treatment group for the RAS.

Categorical data will be presented as frequencies and percentages. For continuous data, mean, standard deviation, median, minimum, and maximum will be presented. For selected parameters, 25th and 75th percentiles will also be presented.

Relevant medical histories and current medical conditions at baseline will be summarized by system organ class and preferred term, by treatment group.

12.3 Treatments

The duration of exposure in days to ruxolitinib and standard of care therapies will be summarized by means of descriptive statistics using the Safety set.

Concomitant medications and significant non-drug therapies prior to and after the start of the study treatment will be listed and summarized according to the Anatomical Therapeutic Chemical (ATC) classification system, by treatment group.

12.4 Analysis of the primary endpoint(s)/estimand(s)

The primary analysis for this study will be conducted on the RAS according the intention to treat principle.

12.4.1 Definition of primary endpoint(s)/estimand(s)

The estimand framework for the primary objective is as follows:

- Treatment - ruxolitinib added to SoC therapy
- Population – Hospitalized patients with coronavirus (SARS-CoV-2) infection confirmed by polymerase chain reaction (PCR) test or another rapid test from the respiratory tract prior to randomization as described in [Section 5.1](#).
- Endpoint - Primary efficacy endpoint is clinical failure, defined as the occurrence of death, respiratory failure (require mechanical ventilation), or ICU care by Day 29.
- Population-level summary - Odds-ratio comparing ruxolitinib added to SoC therapy to placebo added to SoC therapy.
- Intercurrent event(s) - Discontinuation of study treatment

12.4.2 Statistical model, hypothesis, and method of analysis

The statistical hypothesis tested for clinical failure is that there is no difference in the proportion of subjects developing clinical failure by Day 29 with ruxolitinib + SoC versus placebo + SoC therapy.

Let p_j denote the proportion of clinical failures by Day 29 for treatment groups j , $j = 0, 1$ where

- 0 corresponds to placebo + SoC
- 1 corresponds to ruxolitinib + SoC

The following statistical hypothesis will be tested to address the primary objective:

$H_0: p_0 = p_1$, $H_1: p_0 \neq p_1$.

The odds of clinical failure will be analyzed by a logistic regression model with treatment group, region (North America, Europe), baseline clinical status based on the 9-point ordinal scale (≤ 4 , ≥ 5), age, and gender as covariates. The estimated odds ratio, p-values, and 95% confidence intervals will be presented.

The study will be considered positive, if ruxolitinib demonstrates a statistically significant greater reduction in clinical failure. This implies observing an odds ratio of < 1 .

12.4.3 Handling of remaining intercurrent events of primary estimand

Discontinuation of study treatment for any reason: Retrieved drop out (RDO) data after study treatment discontinuation will be collected. If RDO data is available up to Day 29 this will be used for analysis. If no RDO data was collected after study treatment discontinuation or the RDO data is not complete to Day 29 then the patient will be considered as a clinical failure, unless they are in one of the scenarios below:

- There was no occurrence of death, mechanical ventilation, nor ICU care in all the available data and patients were discharged from the hospital
- The last available data (either on-treatment or off-treatment) is from Day 15 or later, and there was no occurrence of death, mechanical ventilation, nor ICU care in all the available data

12.4.4 Handling of missing values not related to intercurrent event

For patients who withdraw from the study, their clinical failure status will be handled similarly as in [Section 12.4.3](#). Other missing data handling rules will be specified in the SAP.

12.4.5 Sensitivity analyses for primary endpoint/estimand

In order to determine the robustness of the logistic regression model used for the primary analysis of clinical failure by Day 29, a non-parametric regression model ([Koch et al 1998](#)) will also be evaluated using the same explanatory variables as the logistic regression model.

12.4.6 Supplementary analysis

To assess the effect of classifying patients' clinical failure status with missing data, a multiple imputation based analysis will be conducted. More details of this approach will be included in the study analysis plan. Other imputation approaches, for example, a worst case analysis, will be considered and may be included in the study analysis plan.

12.4.7 Supportive analyses

The primary analysis of the clinical failure will be repeated for each of the events in the composite endpoint: occurrence of death, mechanical ventilation, and ICU care. Separate logistic regression models will be fitted to compare the odds between treatment groups for each of the endpoints. The analysis will be performed for both Days 15 and 29.

As there is uncertainty around the covariates to be included in the primary analysis model for the clinical failure by Day 29, analyses will be performed considering additional covariates, for example, co-morbidities. These analyses will be defined further in the study analysis plan.

12.5 Analysis of secondary endpoints/estimands

12.5.1 Efficacy and/or Pharmacodynamic endpoint(s)

Full details of all planned analyses will be included in the study analysis plan. However, a brief description of the approaches used for each endpoint are given below.

12.5.1.1 9-category ordinal scale

The odds of observing a better category (lower number) of clinical status (9-category ordinal scale, [WHO 18-Feb-2020](#)) at Day 15 will be analyzed with a proportional odds model (POM). The odds ratio for treatment group (ruxolitinib + SoC therapy vs. placebo + SoC therapy) estimated from the POM can be interpreted as a summary of the odds ratios obtained from separate binary logistic regressions using all possible cutoff points of the ordinal outcome (e.g. the cutoff of level 5 ‘Non-invasive ventilation or high-flow oxygen’ will combine levels 0, 1, 2, 3, and 4 versus combined levels 5, 6, 7 and 8). The assumption of POM is that the effect of treatment is identical across all possible cutoff points of the ordinal outcome. The proportional odds assumption will be checked by a score test. The model will include treatment group, country, age, gender, and baseline clinical status as covariates. The estimated odds ratios, p-values and 95% confidence intervals will be presented. The analysis will be repeated for the data at Day 29.

The treatment groups will also be compared in terms of at least a one-point improvement, at least a two-point improvement, and at least a one-point deterioration in clinical status at Days 15 and 29 using respective logistic regression models with the same covariates as for the POM.

Time to improvement from baseline category to one less severe category of the ordinal scale will be analyzed using a competing risk analysis framework (death will be treated as a competing risk). Baseline clinical status will also be included in the model.

Mean change from baseline in the clinical status on the 9-point ordinal scale to Days 15 and 29 will be summarized by treatment arm. This endpoint will also be analyzed using an analysis of covariance (ANCOVA) model with factors for treatment group and country, as well as the baseline clinical status as a continuous linear covariate.

12.5.1.2 Oxygen saturation

The proportion of patients with no oxygen therapy (defined as oxygen saturation $\geq 94\%$ on room air) at Days 15 and 29 will be analyzed separately using a logistic regression model with the same covariates as for the primary analyses, with baseline oxygen therapy status included.

12.5.1.3 In-hospital outcomes

Duration of hospitalization will be analyzed using a competing risk analysis framework (death will be treated as a competing risk). More details will be provided in the statistical analysis plan. The analyses of mortality rates at Day 15 and at Day 29, and proportion of patients requiring mechanical ventilation by Day 29 are described in [Section 12.4.7](#).

12.5.1.4 National Early Warning Score (NEWS2)

Time to discharge or to a National Early Warning Score (NEWS2) of ≤ 2 and maintained for 24 hours (whichever comes first) will be analyzed using a competing risk analysis framework (death will be a competing risk) ([Royal College of Physicians 2017](#)). The model will also include treatment group, age, and gender (in the case of the analysis of NEWS2, the baseline NEWS2 score will also be included).

Change from baseline to Days 3, 5, 8, 11, 15, and 29 in the National Early Warning Score (NEWS2) and change from baseline to Days 15 and 29 in SpO₂/FiO₂ ratio will be summarized by treatment arm.

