	To evaluate the efficacy of ruxolitinib + SoC therapy, compared with placebo + SoC therapy, in change in SpO ₂ /FiO ₂ ratio in patients with COVID-19.	Change from baseline to Days 15 and 29 in SpO ₂ /FiO ₂ ratio.
	To evaluate the efficacy of ruxolitinib + SoC therapy, compared with placebo + SoC therapy, in proportion of patients with no oxygen therapy (defined as oxygen saturation $\geq 94\%$ on room air) in patients with COVID-19.	Proportion of patients with no oxygen therapy (defined as oxygen saturation $\geq 94\%$ on room air) at Days 15 and 29.
	To evaluate the safety of ruxolitinib + SoC therapy, compared with placebo + SoC therapy, in the treatment of patients with COVID-19.	Number of participants with treatment-related adverse events (as assessed by Common Terminology Criteria for Adverse Event version 5.0), serious adverse events, clinically significant changes in laboratory measures and vital signs during the 29-day Study Period.
[REDACTED]	[REDACTED]	[REDACTED]
[REDACTED]	[REDACTED]	[REDACTED]

The study will include:

- **Screening period** of 0-2 days
- **Study period** of 29 days (treatment of 14 days; an additional 14 days of study drug may be given, if in the opinion of the investigator, the patient's clinical signs and symptoms are not improved or worsen and the potential benefit outweighs the potential risk) – see below.

Figure 3-1 Study design

Note: Should a patient become intubated during the Study Period, study medication may be given via a nasogastric tube (see [Section 6.1.1](#) for directions).

Eligible patients will be randomized on the same day as screening or up to two days after completing the screening procedures. At Day 1 (randomization visit), patients will be assigned in a 2:1 ratio to receive oral ruxolitinib 5 mg twice daily or oral matching-image placebo for a total of 14 days ([Section 6.1](#)). An additional 14 days of study drug may be given, if in the opinion of the investigator, the patient's clinical signs and symptoms are not improved or worsen and the potential benefit outweighs the potential risk.

Study treatment will be given in combination with SoC therapy according to the investigator's clinical judgement. Should a patient become intubated during the Study Period, study medication may be given via a nasogastric tube (see [Section 6.1.1](#) for directions). Randomization will be stratified by region (North America, Europe).

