##### 2.1.1.3 Post-baseline measurement

Post-baseline measurements are defined as those assessments after the first dose of double-blind treatment.

When change from baseline is of interest the following formula will be used for each scheduled visit and time-point where baseline and post-baseline values are both available:

Change from baseline = post-baseline value – baseline value.

If not stated otherwise for efficacy analyses, on-treatment values are defined as values taken post-baseline but no later than 1 day after last dose of double-blind treatment. Off-treatment values are defined as post-baseline values taken more than 1 day after last dose of double-blind treatment. All on- and off- treatment values will be used in the efficacy analyses, unless otherwise specified.

For safety analyses other than adverse events (AEs), e.g. laboratory, vital signs, treatment-emergent values are defined as values taken post-baseline and up to the last study visit (Day 29).

AEs will be considered as treatment-emergent if the event starts after the first dose of double-blind treatment or the event is present prior to start of double-blind treatment but increased in severity based on preferred term and up to the last study visit (Day 29).

Details on calculation of post-baseline values are provided in the latter sections.

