#### Change from baseline

Mean change from baseline in the clinical status on the 9-point ordinal scale to Days 15 and 29 will be analyzed using an analysis of covariance (ANCOVA) model with factors for treatment

group, age, gender, and region, as well as the baseline clinical status as a continuous linear covariate. The estimated treatment differences, p-values, and 95% CIs will be presented.

Missing data at Day 15/29 will not be imputed and thus will be excluded from the analysis.

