#### **2.7.1.5 SpO2/FiO2 ratio**

Summary statistics of change from baseline to Days 15 and 29 in SpO2/FiO2 ratio will be provided by treatment. In addition, the following categorization will be done:

- Severity of acute respiratory distress syndrome (ARDS): normal:  $> 314$ ; mild (235 - 314); moderate: 150 - 234; severe:  $< 150$

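### The SpO2/FiO2 objective is the only secondary efficacy objective with no planned between-arm estimate, and its by-arm summaries have no place for patients who died

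*Protocol*

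**What the plan says.** The objective is comparative. Protocol Table 2-1 sets out to evaluate efficacy "compared with placebo + SoC therapy, in change in SpO ₂ /FiO ₂ ratio in patients with COVID-19", with change from baseline to Days 15 and 29 as its only endpoint. SAP Table 1-1 repeats this.

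The analysis is descriptive. Protocol 12.5.1.4 states that "change from baseline to Days 15 and 29 in SpO₂/FiO₂ ratio will be summarized by treatment arm". Protocol 12.5.1 leaves room for more: "Full details of all planned analyses will be included in the study analysis plan". SAP 2.7.1.5, which is readable and not redacted, plans "Summary statistics of change from baseline to Days 15 and 29 in" the ratio, by treatment. It also plans a four-level grouping that begins "Severity of acute respiratory distress syndrome (ARDS): normal" (above 314), followed by mild (235 to 314), moderate (150 to 234) and severe (below 150). It gives no model, treatment difference, interval, test or rule for deaths. SAP Section 4 lists no change for this endpoint.

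SAP 2.1.1.3 computes change "for each scheduled visit and time-point where baseline and post-baseline values are both available". For mean change on the 9-point scale, by contrast, SAP 2.7.1.1 specifies an ANCOVA and says "The estimated treatment differences, p-values, and 95% CIs will be presented".

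**The concern.** The plan poses a between-arm question and pre-specifies no between-arm answer. Anyone who wants one must subtract two arm means. That contrast ignores the baseline ratio and counts only patients who have a value on the day.

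The second feature matters in a disease with mortality. A patient who has died has no ratio. If one arm keeps alive more of the patients who would otherwise have died, and those patients recover less well, they enter that arm's mean only. The arm with fewer deaths then looks worse on oxygenation. The ARDS table does not help, because it has no row for death.

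What is at stake is one secondary objective. The primary analysis, its power and its type I error are untouched.

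**Working it through.** **1. The secondary efficacy objectives side by side (SAP 2.5.4 and 2.7.1)**

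| Objective | Planned between-arm analysis | Death |
|---|---|---|
| 9-point scale | Proportional odds, logistic, ANCOVA, Fine-Gray | Score 8 on the scale; competing risk in time to improvement |
| In-hospital outcomes | Logistic models and risk differences; Fine-Gray for discharge | An outcome itself, or a competing risk |
| NEWS2 | Fine-Gray for time to discharge or score ≤ 2; change is summarized only | Competing risk in the model |
| No oxygen therapy | Logistic, with baseline SpO2/FiO2 as a covariate | No separate rule; missing values excluded |
| SpO2/FiO2 ratio | None | No rule, and no ARDS category |

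The exclusion of the dead is inferred from the general rule in SAP 2.1.1.3, since 2.7.1.5 is silent on missing values.

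**2. Is an estimate feasible at the planned size?** The documents give no figure and no SD for this endpoint, so results are in SD units of the change. Allocation is 268 and 134 (SAP 1.1). As a check on those numbers, the unpooled two-proportion normal approximation at two-sided 0.05 gives 91.3, 85.2, 82.1, 82.1, 85.2 and 91.3%. This matches all six rows of Protocol Table 12-1 for the primary endpoint. The present point does not depend on that table.

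For a difference in means, the half-width is 1.96 × √(1/n_placebo + 1/n_ruxolitinib). The share without a value is assumed equal in both arms:
- 0%: 1.96 × √(1/134 + 1/268) = 0.207 SD
- 5%: 0.213 SD
- 10%: 0.219 SD
- 15%: 1.96 × √(1/113.9 + 1/227.8) = 0.225 SD

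The difference detectable with 80% power runs from 0.296 SD (0%) to 0.322 SD (15%). A useful interval is available.

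**3. Gain from baseline adjustment.** Assume equal variances at baseline and follow-up, with correlation ρ. Then Var(ANCOVA) / Var(raw change difference) = (1 − ρ²) / [2(1 − ρ)] = (1 + ρ)/2.
- ρ = 0.2: 0.60, a 40% cut in variance
- ρ = 0.6: 0.80, a 20% cut

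**4. Survivor distortion.** Assume the change each patient would show if alive has the same normal distribution (SD 1) in both arms, and that deaths come from its worst tail. With death proportion d, the survivor mean is φ(z_d)/(1 − d). This is 0.049 at d = 2%, 0.109 at 5%, 0.195 at 10% and 0.274 at 15%. Ruxolitinib minus placebo among survivors is then:

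| Deaths, placebo / ruxolitinib (assumed) | Difference (SD) |
|---|---|
| 5% / 2% | −0.059 |
| 10% / 5% | −0.086 |
| 15% / 10% | −0.079 |
| 10% / 10% | 0 |
| 5% / 10% | +0.086 |

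The sign always goes against the arm with fewer deaths. The size is less than half of the interval half-width in step 2.

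**5. Does ranking death worst repair the direction?** Take 10% against 5% deaths, and suppose survivors in the two arms have identical distributions. The probability that a ruxolitinib patient does better (ties counted as half) is 0.95 × 0.10 + 0.5 × (0.90 × 0.95 + 0.10 × 0.05) = 0.525. Under the tail model of step 4 it is 0.5 × 0.05 × 0.10 + 0.05 × 0.10 + 0.90 × 0.10 + 0.5 × 0.90² = 0.5025. Both are above 0.5, so the ranking favors the arm with fewer deaths.

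**The case against.** The strongest reply is that little is lost. By-arm summaries of a randomized comparison allow an unadjusted difference, with an interval if means, SDs and numbers are shown. The 9-point scale is graded largely by oxygen support and includes death. Freedom from oxygen therapy, ventilation and mortality all have models, so a mortality difference would not go unseen. Describing change in both physiological measures, NEWS2 and SpO2/FiO2, is consistent across protocol and SAP. No secondary endpoint has multiplicity control. An ANCOVA would also use only patients with values.

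Much of this stands. A reader might infer that the trial yields no information on this treatment effect, or that the objective is unanswerable. The documents do not support that, because the arm summaries permit a crude contrast. A reader might also infer a large survivor bias. No mortality, SD or SpO2/FiO2 mean is given from which to show one, and SAP Section 4 says few patients entered at baseline status 5. The point about ANCOVA is right too: alone it does not address death.

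Two things remain. The neighboring models answer other objectives; none estimates change in SpO2/FiO2, and in the no-oxygen model the ratio is only a baseline covariate. The NEWS2 parallel is also incomplete, because that objective has a comparative model with death as a competing risk and this one has none.

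**Conclusion.** The point holds in a limited form. The plan specifies no between-arm estimate, interval or test for the SpO2/FiO2 objective, and no other secondary efficacy objective lacks all three. Any difference derived from the arm summaries would be unadjusted and confined to patients with both values.

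The consequence is modest. The survivor distortion of about 0.06 to 0.09 SD rests on assumed mortality differences of 3 to 5 points, a common latent distribution and deaths drawn from its worst tail. It is zero with equal mortality. The 20 to 40% variance gain rests on assumed equal variances and ρ of 0.2 to 0.6. The gap itself rests on the text alone. It is worth closing because the repair is cheap and lets the trial answer a question it sets itself.

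**What to change.** In SAP 2.7.1.5, for Day 15 and Day 29:

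1. Add the ANCOVA form of SAP 2.7.1.1, with treatment, age, gender and region, and baseline SpO2/FiO2 as a continuous covariate. Report the adjusted difference with 95% CI, labelled as an analysis of patients with values.
2. Pair it with a rank-based analysis that places patients dead by that day at the worst rank.
3. Add a death category to the ARDS severity table.
4. Keep the descriptive tables, and state that the results are supportive because secondary endpoints have no multiplicity adjustment (SAP 2.7.1).

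Extending this to NEWS2 change is optional, since that objective already has a comparative model in SAP 2.7.1.4.

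The cost is SAP wording, two models at each of two days and one table row. Protocol Table 8-1 already schedules SpO2 and FiO2 at Day 1, Day 15 and Day 29, including for discharged patients, so no new data are needed. The change should be made before database lock, while treatment is still blinded.
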